### *Investigator evaluation of Injection Site Reactions*

The injection site reactions are reported as part of the TEAEs. For each subject with an injection site reaction, subject profiles will be produced that summarize corresponding adverse event data along with demographic variables, dose of study drug, duration of exposure, drug discontinuation, CRP and eosinophil levels and medications used to treat the injection site reaction

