2 STUDY OBJECTIVES

2.1 PRIMARY OBJECTIVE:

- The Primary objective of this study is to assess the efficacy of Leronlimab (PRO 140) in improving liver function in adult patients diagnosed with NASH compared to placebo

2.2 SECONDARY OBJECTIVE:

- The Secondary objective of this study is to assess the safety and tolerability of Leronlimab (PRO 140) in adult patients diagnosed with NASH compared to placebo

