- [12] Urine samples will be tested for pH, appearance, color, specific gravity, turbidity, ketones, bilirubin, occult blood, glucose, protein, nitrites, urobilinogen, and leukocyte esterases. Microscopic examination of urine sediment will be performed if there are abnormalities in macroscopic urinalysis results. Microscopic urine tests include bacteria, cast, crystals, epithelial cells, RBC and WBC.
- [13] Only performed on women of childbearing potential
- [14] Blood sample collected at T1 (prior to first dose of PRO 140), pre-dose at T2, T6, T10, and at EOT (or ET) and Follow-up visit
- [15] Randomization via WebView CTMS system only applicable for Part 1 of the study
- [16] Leronlimab (PRO 140) or placebo is administered as subcutaneous injection in the abdomen weekly. In Part 1 of the study, a total of 700 mg dose of leronlimab (PRO 140) or placebo will be delivered as two injections of 2 mL. In the Part 2 of the study, a total dose of 350 mg dose of leronlimab (PRO 140) will be delivered as one injection of 2 mL.
- [17] Injection Site Reaction Assessment as assessed by Investigator (or designee) at the clinic .
- [18] Subject-perceived injection site pain (average pain since last treatment) will be assessed using 11-point Numeric Rating Scale from 0 to 10 prior to each study treatment administration. "0" meaning "no pain" and "10" meaning "worst possible" pain.
- [19] AE and CM evaluations to be conducted at each clinic visit applicable
- [20] Subjects discontinuing the study at any time for any reason (early termination-ET) should complete the procedures listed AND the follow-up visit
- [21] In case subjects have already completed their EOT/ET and FU visits, site should use the Unscheduled Visit option to collect blood sample for Monocyte/T Cell CCR5 analysis.

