6 STUDY TREATMENT

6.1 INVESTIGATIONAL PRODUCT

In Part 1 of the study, Leronlimab (PRO 140) or placebo will be administered subcutaneously (SC) at a weekly dose for 13 weeks. In Part 2 of the study, Leronlimab (PRO 140) will be administered as a 350 mg, weekly dose for 13 weeks.

Table 6-1: Treatment Administration Summary

Part 1:

Study Group	Study Drug	Dose	Route	Schedule
A	Leronlimab (PRO 140)	700 mg	SC	Start on Day 1 and every week thereafter
B	Placebo	N/A	SC	Start on Day 1 and every week thereafter

Part 2:

Study Group	Study Drug	Dose	Route	Schedule
C	Leronlimab (PRO 140)	350 mg	SC	Start on Day 1 and every week thereafter

Leronlimab (PRO 140)

Leronlimab (PRO 140) is a humanized IgG4,κ Monoclonal Antibody (mAb) to the chemokine receptor CCR5. Leronlimab (PRO 140) is provided at a concentration of 175 mg/mL and is intended for SC route of administration.

Part 1:

In Part 1 of the study, for Group A (Leronlimab 700 mg), one study injection kit will be assigned per subject per treatment visit. Leronlimab kits will be labeled with a unique identification number. Each kit used during the Treatment Period will contain two vials of Leronlimab (PRO 140) for SC injection.

Each vial of the Leronlimab (PRO 140) product contains ~2.4 mL antibody at 175mg/mL in a buffer containing [REDACTED] L-histidine, [REDACTED] glycine, [REDACTED] sodium chloride, [REDACTED] sorbitol, [REDACTED] polysorbate 20 (Tween 20®), and sterile water for injection, at pH of [REDACTED].

Note: For Group A (Leronlimab (PRO 140 at 700 mg), 2 mL will be drawn from 2.4 mL solution filled vial. Remaining 0.4 mL medication will be discarded appropriately from each vial.

Placebo

For Group B, Isotonic 0.9% Sodium Chloride Injection, USP will be used as placebo.

A dose of 700 mg of Leronlimab (PRO 140) (175 mg/mL) or placebo will be delivered as two injections of 2 mL each and administered subcutaneously on opposite sides of the abdomen.

Note: *The IP preparations mentioned above will be conducted by the unblinded pharmacist or qualified designated unblinded site staff. The IP administrations will be conducted by blinded designated site staff.*

Table 6-2: Part 1: Investigational Product - Leronlimab (PRO 140) or Placebo

Study Group	IP Dosage	Dosage Form	IP concentration	Dosing Frequency and Amount	Route of Administration
A	PRO 140 700 mg	Parenteral solution	175 mg/mL	2 injections of PRO 140 (2 mL/inj.) per week on opposite sides of abdomen	SC injection

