B	Placebo	Parenteral solution	0 mg/mL	2 injections of Placebo (2 mL/inj) per week on opposite sides of abdomen	SC injection

Note: *Patients with low body fat percentages may find subcutaneous injections uncomfortable. In such cases, Leronlimab (PRO 140) or placebo can be injected at different areas other than abdomen as per discretion of the Investigator.*

Part 2:

In Part 2 of the study, (Leronlimab 350 mg), one study injection kit will be assigned per subject for two treatment visits. Leronlimab kits will be labeled with a unique identification number. Each kit used during the Treatment Period will contain two vials of Leronlimab (PRO 140) for SC injection.

Table 6-3: Part 2: Investigational Product - Leronlimab (PRO 140)

Study Group	IP Dosage	Dosage Form	IP concentration	Dosing Frequency and Amount	Route of Administration
C	PRO 140 350 mg	Parenteral solution	175 mg/mL	1 injection of PRO 140 (2 mL/inj.) per week in the abdomen area	SC injection

Note: *For group C (Leronlimab (PRO 140 at 350 mg), 2 mL will be drawn from 2.4 mL solution filled vial. Remaining 0.4 mL medication will be discarded appropriately from each vial.*

A dose of 350 mg of Leronlimab (PRO 140) (175 mg/mL) will be delivered as one injection of 2 mL and administered subcutaneously in the abdomen.

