### 2.2 Study Design

This is a phase II, multi-center, two-part study.

[figure not shown]
- Part 1. Randomized, double-blind, placebo-controlled, two-arm with 60 patients designed to evaluate the safety, tolerability, and efficacy of leronlimab (PRO 140 700mg dose) or placebo weekly administered subcutaneously (SC) in patients with NASH for 13 weeks.
- Part 2. Non-randomized, single-arm, open-label with 30 patients designed to evaluate the safety, tolerability, and efficacy of leronlimab (PRO 140 350mg dose) weekly administered subcutaneously (SC) in patients with NASH for 13 weeks SC in patients with NASH for 13 weeks

For Part 1 of the study leronlimab 700mg group will be compared to placebo.

For Part 2 of the study leronlimab 350mg group will be compared to placebo from Part 1.

[figure not shown]
The study schematic is presented in Figure 2.1 and Figure 2.2

Figure 2.1: Study Schematic

	STATISTICAL ANALYSIS PLAN (SAP)		
	CD1-NASH-01	Protocol No. CD1-NASH-01	Revision No. Rev. 00

Figure 2.2

See Section 3.3 in the protocol for eligibility and exclusion.

Subjects who complete the treatment period will continue to End of Treatment (EOT) Visit assessments at week 14 and enter the Follow-up Phase of the study. Subjects who meet any criteria for discontinuation of study treatment as specified in Section 5.1 of the protocol, will undergo Early Termination (ET) Visit assessments 7 days after the last injection and enter the Follow-up Phase of the study.

A Follow-up visit will be conducted 28 ( $\pm$  3) days after the End of Treatment (EOT) or Early Termination (ET) Visit.

See Table 4-2 of the protocol for detailed study schedule.

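### Injection-site reactions are tabulated per subject only, although 350 mg subjects get one injection a week and placebo and 700 mg subjects get two; a rate per injection and a footnote would make the contrasts readable.

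*SAP*

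**What the plan says.** Protocol Table 6-2 gives the placebo group "2 injections of Placebo (2 mL/inj) per week on opposite sides of abdomen" and the 700 mg group "2 injections of PRO 140 (2 mL/inj.) per week on opposite sides of abdomen". Table 6-3 gives the 350 mg group "1 injection of PRO 140 (2 mL/inj.) per week in the abdomen area". Footnote 16 to Protocol Table 4-2 agrees: the Part 1 dose "will be delivered as two injections of 2 mL", the Part 2 dose "will be delivered as one injection of 2 mL".

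Placebo is the reference for tolerability. The secondary objective (Protocol 2.2, repeated in SAP 2.1) is to "assess the safety and tolerability of Leronlimab (PRO 140) in adult patients diagnosed with NASH compared to placebo". SAP 2.2 states as a general design point: "For Part 2 of the study leronlimab 350mg group will be compared to placebo from Part 1".

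On reporting, SAP 9.3.7 says "The injection site reactions are reported as part of the TEAEs" and adds a profile for each affected subject. SAP 9.3.2 gives a listing of injection-site reactions as events of special interest. Its adverse event summary table has one column each for placebo, 700 mg and 350 mg, filled with subject counts and percentages. No output uses injections given as the denominator, and no note tells the reader that injection number differs between columns. The adverse event, exposure and pain tables have no difference or p-value column.

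**The concern.** The chance that a subject has at least one injection-site reaction rises with the number of injections. The 700 mg group and placebo have the same number, so that contrast is fair on this point. The 350 mg group has half as many as the placebo group it is set beside. If its injections carried the same local risk as saline, a smaller share of its subjects would still be expected to have a reaction. A moderate excess per injection could go unseen.

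The same applies to 350 mg against 700 mg. Each active injection is the same, 2 mL at 175 mg/mL, so the local difference between the two regimens is the number of sites injected. In a study titled dose-ranging, a difference in affected subjects could be read as a dose effect on local tolerability when injection number alone could produce it. This would remain even if Part 2 had been randomised against the same placebo.

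**Working it through.** The plan has no figure of its own to reproduce: the sample size rests on clinical judgment and no reaction rate is given. The check is therefore an illustration on stated assumptions.

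**Inputs from the documents**
- Concentration 175 mg/mL, 2 mL per injection, 13 weekly doses (Protocol 6.1).
- Dose check: 175 × 2 × 2 = 700 mg; 175 × 2 × 1 = 350 mg.
- Injections if all doses are given: 13 × 2 = 26 for placebo and 700 mg; 13 × 1 = 13 for 350 mg. Ratio 13/26 = 0.5.
- 30 subjects per arm in Part 1, up to 30 in Part 2 (Protocol 8.3).

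**Assumptions, not in the documents**
- Risk q of a reaction at each injection, equal in all groups, so that any gap comes from injection number alone. Range 0.5% to 10%.
- Intra-subject correlation ρ between injections. Values 0 to 0.5.

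**Formulas**
- Independent injections: P(at least one reaction) = 1 − (1 − q)^m, with m = 13 or 26.
- Correlated injections (beta-binomial): P = 1 − B(a, b + m)/B(a, b), where a = q(1/ρ − 1), b = (1 − q)(1/ρ − 1) and B is the beta function.

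**Independent injections**

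| q | 350 mg (13) | Placebo (26) | Ratio |
|---|---|---|---|
| 0.5% | 6.3% | 12.2% | 0.52 |
| 1% | 12.2% | 23.0% | 0.53 |
| 2% | 23.1% | 40.9% | 0.57 |
| 5% | 48.7% | 73.6% | 0.66 |
| 10% | 74.6% | 93.5% | 0.80 |

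For q = 2%: 1 − 0.98^13 = 0.231 and 1 − 0.98^26 = 0.409, or about 7 against 12 of 30 subjects.

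**Effect of correlation at q = 2%**

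| ρ | 350 mg | Placebo | Ratio | Break-even multiple |
|---|---|---|---|---|
| 0 | 23.1% | 40.9% | 0.57 | 1.98 |
| 0.05 | 18.4% | 28.5% | 0.65 | 1.64 |
| 0.2 | 11.7% | 15.7% | 0.74 | 1.37 |
| 0.3 | 9.3% | 11.9% | 0.78 | 1.30 |
| 0.5 | 6.2% | 7.4% | 0.83 | 1.21 |

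The break-even multiple is how many times the placebo risk per injection the 350 mg risk would have to be before the expected per-subject percentages were equal. At q = 5% and ρ = 0.3 the percentages are 21.8% against 27.3%.

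**Set against sampling error.** At q = 2% and ρ = 0.3 the gap is 0.093 × 30 = 2.8 against 0.119 × 30 = 3.6 subjects. The approximate 95% half-width for that difference is 1.96 × √[(0.093 × 0.907 + 0.119 × 0.881)/30] ≈ 0.16, or 16 percentage points. The injection-number component has the same sign in every case examined, but with strong clustering it is small beside the noise.

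**The case against.** The strongest reply is that the 350 mg regimen is one injection a week, so the share of its subjects with a reaction is exactly what a patient on that regimen would face. That stands. A reader might infer that the tables would make 350 mg look better tolerated than it is, or that the whole gap would be artefact. The documents support neither: the column is right for its own regimen, and only the contrast with a two-injection group is affected.

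A reader might also infer that the overall bias runs in favour of 350 mg. That is not established. Part 2 is open-label and non-randomised while Part 1 is blinded (Protocol 8.4 and 8.5, SAP 2.8), and knowing that the injection is active could raise reporting. This second influence is unmeasured; it neither cancels the first nor can be assumed smaller.

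No formal safety test is planned. SAP 9.1 ties formal comparisons to the full analysis and per-protocol sets, not the safety set. A modelled comparison would go beyond the plan and be fragile with few affected subjects. What remains is that the objective is worded against placebo and the columns sit side by side, so they will be compared by eye.

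Protocol 1.5 reports that in the three-part HIV maintenance study reactions were no more frequent or severe at higher doses. It does not say how many injections each dose took, so it settles nothing either way.

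It is tempting to extend the argument to the pain table in SAP 9.3.7. The score is an average intensity since the last treatment (Protocol Table 4-2, footnote 18), not the occurrence of at least one event, so the calculation does not carry over.

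Finally, the subject profiles show dose and duration of exposure, and injection numbers can be found in Protocol Tables 6-2 and 6-3. That helps a careful reader, but puts no denominator or caveat on the summary table.

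**Conclusion.** The point holds as a cheap improvement, not as an error that invalidates an analysis. Injection number differs by a factor of two between 350 mg and both Part 1 groups, and the only summary of injection-site reactions is per subject. The injection-number component of the 350 mg contrasts therefore favours 350 mg relative to a matched-injection control. Assuming equal risk per injection, full dosing and a 2% risk, it ranges from 23% against 41% with independent injections to about 9% against 12% at correlation 0.3. Neither the risk nor the correlation is in the documents, so the true size is unknown. Nor is the net direction of the observed contrast, given the open label and lack of randomisation. The 700 mg against placebo contrast is unaffected.

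**What to change.** In SAP 9.3.7, add a descriptive table of injection-site reaction events per 100 injections administered, overall and by CTCAE grade, for all three groups. Give each rate a confidence interval that allows for repeated injections within a subject, for example by resampling subjects. No formal count-model comparison is needed.

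Keep the per-subject TEAE table. Footnote it to say that 350 mg subjects received one injection a week, unblinded and non-randomised, against two in the blinded Part 1 groups, so contrasts between those columns are descriptive and not like-for-like.

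The cost is one table, one footnote and a counting rule. Dosing data must already be held to apply the 80% compliance criterion, and Protocol 7.11 has current and previous injection sites assessed at each treatment visit. The adverse event fields in Protocol 9.2 do not include the side injected, so the SAP should say how reactions at both sites on one visit are counted. The downside is that events must be counted per injection and the 350 mg column may look less favourable. No dose, schedule or clinical rule changes.

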Post Injection Site Evaluation by Investigator ^[17]			X	X	X	X	X	X	X	X	X	X	X	X	X		
Injection Site Pain Assessment ^[18]				X	X	X	X	X	X	X	X	X	X	X	X		
Concomitant medications ^[19]	X	X		X	X	X	X	X	X	X	X	X	X	X	X	X	X
Adverse Events ^[19]			X	X	X	X	X	X	X	X	X	X	X	X	X	X	X

- [1] Informed consent must be obtained prior to patient participation in any protocol-related activities that are not part of routine care.
- [2] A complete review of the subject's past medical history (liver disease), history of prior symptoms or concurrent diseases (including liver disease), past surgeries, and current therapies (medications and non-medications) will be undertaken
- [3] Vital signs including blood pressure, heart rate, respiration rate, and temperature will be measured at each clinic visit.
- [4] Weight only on visits T1 (Pre-Treatment), T2, T6, T10 and EOT/ET
- [5] Symptom-directed physical examination at clinic visits
- [6] A 12-lead ECG will be repeated during the study
- [7] FibroTest (requires fasting for 12 hours or more) combines 5 standard biomarkers (gamma-glutamyltransferase, total bilirubin, alpha-2-macroglobulin, apolipoprotein A1, and haptoglobin). The Acti-Test adds a marker for inflammatory activity (alanine aminotransferase: ALT). These markers are weighted depending on the patient's age and gender.
- [8] Fibroscan or equivalent non-invasive imaging test is acceptable
- [9] Liver MRI will be performed to evaluate MRI-derived biomarkers such as proton density fat fraction (PDFF) and corrected T1 (cT1).
- [10] Hemoglobin, Hematocrit (HCT), Red Blood Cells (RBC), White Blood Cells (WBC) with total and differential count, absolute lymphocyte count, absolute neutrophil count (ANC) and platelets.
- [11] Serum Biochemistry will include:
 - Hepatic function/NASH indicators: Total bilirubin, Direct bilirubin, alkaline phosphatase, aspartate aminotransferase (AST)/SGOT, alanine aminotransferase (ALT)/SGPT, Prothrombin Time (PT), International Normalized Ratio (INR), albumin, total protein, Triglycerides, Cholesterol (Low density lipoprotein), creatine kinase, Gamma-glutamyltransferase (GGT), and serum CK-18
 - Renal function indicators: blood urea nitrogen (BUN), creatinine, eGFR
 - Electrolytes: sodium, potassium, chloride, calcium and bicarbonate

Other: Fasting blood Glucose , Serum HbA1C, Thyroid profile

Note: Screening laboratory testing can be repeated once during the 28-day screening window based on the Investigator's clinical judgement).

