7.11 POST-INJECTION EVALUATION AND INJECTION SITE REACTION ASSESSMENT

[figure not shown]
At each treatment visit, an injection site reaction assessment will be made for the current and previous injection sites. Injection site reaction assessments are recorded by the Investigator starting after the first injection is given. Subject will be observed at approximately 30 minutes post-injection or longer if necessary for injection site reaction as per CTCAE v5.0. Refer to [Sections 0](#) for more details.

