9.1 ADVERSE EVENT (AE)

An adverse event (AE) is defined as any unfavorable or unintended sign, symptom, or disease that occurs or is reported by the subject to have occurred, or a worsening of a pre-existing condition. An adverse event may or may not be related to the study treatment.

AEs will be elicited through direct questioning and subject reports. Any abnormalities in visit evaluations, physical examination findings or laboratory results that the investigator believes are clinically significant to the research subject and that occurred after initiation of the first study treatment will be reported as AEs. Abnormal findings that are NOT clinically significant should be not be recorded as an AE.

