The outcome of the event will be assessed as either: fatal, not recovered/not resolved, recovered/resolved, recovered/resolved with sequelae, recovering/resolving, and unknown. Only one AE per subject is allowed to have an outcome assessment as “death.” If there are multiple causes of death for a given subject, only the primary cause of death will have an outcome of death

Injection-site reactions

Injection-site reactions thought to be directly related to the injection are considered to be AEs of special interest, and will be assessed as per CTCAE v5.0.

For subjects who develop Grade 1 or Grade 2 events, therapy will be continued as per protocol. If a subject chooses to discontinue study treatment, the site should notify the protocol team leadership, and encourage the subject to complete any remaining study visits until the toxicity resolves.

For subjects who develop Grade 3 events following study drug injection, the subject should be reevaluated closely until the AE returns to Grade 1 or less, at which time study treatment may be reintroduced at the discretion of the site investigator. If the same Grade 3 AE recurs following the next administration of study drug, study treatment must be permanently discontinued. Subjects experiencing Grade 3 AEs requiring permanent discontinuation of study treatment should be followed closely for resolution of the AE to Grade 1 or less and the team leadership must be notified.

For Grade 4 events permanently discontinue therapy.

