### 3.4 Safety Endpoints

Safety endpoints of the study are:

- Adverse events (AEs)
- Laboratory parameters (blood tests, urinalysis)
- Vital signs (blood pressure, heart rate)
- Subject's medical condition (physical examination including weight)
- Tolerability of repeated subcutaneous administration of Leronlimab (PRO 140) will be assessed by
  - Subject rated 11-point Numeric Pain Rating Scale
  - Investigator-evaluation of injection site reactions.

	STATISTICAL ANALYSIS PLAN (SAP) CD1-NASH-01		
	Protocol No. CD1-NASH-01	Revision No. Rev. 00	Effective Date: 17-Dec-2021

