### 9.3.7 Tolerability

Tolerability of repeated injections will be assessed by

- Subject rated 11-point Numeric Pain Rating Scale (0=None to 10=Worse)
- Investigator-evaluation of injection site reactions

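### SAP 9.3.7 summarises the investigator's injection-site evaluation only through adverse-event records, and no summary table shows reactions by visit over the 13 weekly doses

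*SAP*

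**What the plan says.** SAP 3.4 introduces the endpoint with "Tolerability of repeated subcutaneous administration of Leronlimab (PRO 140) will be assessed by" and names two measures: the subject's pain score and the investigator's evaluation of reactions. SAP 9.3.7 repeats the second as "Investigator-evaluation of injection site reactions".

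The protocol provides an examination for it. Section 7.11 states: "At each treatment visit, an injection site reaction assessment will be made for the current and previous injection sites". It continues: "Injection site reaction assessments are recorded by the Investigator starting after the first injection is given". Table 4-2 carries the row "Post Injection Site Evaluation by Investigator", marked after dosing at T1 and then at every visit T2 to T13. Under Tolerability, Protocol 8.8 commits to both listing and summarising injection-site reactions.

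The SAP's whole treatment of the measure is that "The injection site reactions are reported as part of the TEAEs", together with a profile for each subject who had a reaction. SAP 9.3.2 adds a subject listing of injection-site reactions as adverse events of special interest.

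Two protocol rules bear on whether a reaction becomes an adverse event. Section 9.1, on abnormal findings in general, says: "Abnormal findings that are NOT clinically significant should be not be recorded as an AE". Section 9.2, on injection-site reactions in particular, says: "Injection-site reactions thought to be directly related to the injection are considered to be AEs of special interest".

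**The concern.** The endpoint asks how subjects tolerate a series of injections. The protocol schedules a repeated examination with a natural denominator at each visit: the subjects injected that day. The SAP replaces it with adverse-event reporting, whose summary tables give one count per term and arm for the whole study. A reader of those tables could not tell whether reactions grow, fade or recur over 13 doses, although the examination that would show it is already scheduled. SAP section 10, which lists changes from the protocol, does not mention this choice.

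A second issue is completeness. If sites differ on whether a minor reaction counts as an adverse event, the summaries reflect recording habit as well as tolerability. Protocol 1.6 describes injection-site reactions as the most common adverse events so far and mostly mild. The question therefore concerns the leading local safety finding, in a trial that compares two injections per visit (Part 1) with one (Part 2).

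**Working it through.** The plan states no figure for this point, so there is none to reproduce. The check is mainly one of text, with small calculations to show what a whole-study count can and cannot display.

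**1. Does any SAP summary table show reactions by visit?**
- SAP 9.3.2 plans four adverse-event summaries: all, drug-related, serious, and leading to withdrawal. The shell has rows for any event, system organ class and preferred term, and columns for arm. It has no visit and no row for subjects with any injection-site reaction.
- Protocol 8.8 also plans a summary by class, term and severity. The four SAP summaries do not include it, so the grade of reactions is not tabulated either.
- The pain table in SAP 9.3.7 pools scores into 0–5, 6–7 and 8–10 by arm, without visit, so it cannot stand in.
- The profiles cover only subjects with a reaction and supply no denominator.

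The answer is no.

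**2. How many scheduled evaluations are concerned?** Inputs are 13 treatment visits (Table 4-2) and 30 subjects per arm (Protocol 8.3).
- Per arm: 13 × 30 = 390.
- Part 1: 13 × 60 = 780. Part 2: 13 × 30 = 390. Total: 1,170 with full attendance.

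These evaluations have no planned by-visit summary. Reactions among them that are entered as adverse events are still analysed as such.

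**3. What does an ever/never count hide, even if every reaction is recorded?** Assume a reaction probability p at each visit, with visits independent. Then P(at least one in 13) = 1 − (1 − p)^13. The documents give no rates, so p is purely illustrative.
- p = 20%: 94.5%, or 28.4 of 30 subjects; 390 × 0.20 = 78 visits with a reaction.
- p = 40%: 99.9%, or 30.0 of 30 subjects; 390 × 0.40 = 156 visits with a reaction.

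Doubling the burden moves the subject count by fewer than two. At low p the count is more responsive (1%: 12.2%; 10%: 74.6%), but it still says nothing about when in the series reactions occur.

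**4. Would incomplete recording bias the arm difference in a known direction?** Use the same formula, with half of the reactions recorded in each arm.
- 40% versus 20% per visit: full recording gives 99.9 − 94.5, about 5 points. Half recording (20% versus 10%) gives 94.5 − 74.6, about 20 points. The difference widens.
- 4% versus 2% per visit: full recording gives 41.2 − 23.1, about 18 points. Half recording (2% versus 1%) gives 23.1 − 12.2, about 11 points. The difference narrows.

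The direction depends on the assumed rates and cannot be derived from the documents.

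**5. Are the two recording rules compatible?** Protocol 9.1 covers abnormalities found in visit evaluations and keeps those that are not clinically significant out of the adverse-event data. The injection-site rule in 9.2 depends on attribution to the injection, sets no clinical-significance condition, and describes what happens with Grade 1 events. A site faced with a faint reaction that it regards as unimportant could follow either rule. The SAP does not say which governs.

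**The case against.** The best defence is that the adverse-event route was meant to capture everything. Protocol 9.2 is specific to these reactions, has no clinical-significance test and includes Grade 1. Table 9-1 lets Grade 1 be an asymptomatic observation, and Table 6-4 has a Grade 1 row. The examination is itself graded by CTCAE, which suggests that it feeds adverse-event recording. For a reaction at the injection site about half an hour after dosing, attribution filters little. This stands. A reader might infer that mild reactions drop out of the data; the documents show only that two rules conflict.

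A reader might also infer that the SAP leaves the evaluation unused. That is too strong. SAP 9.1 lists collected data by subject, and the listing of injection-site reactions gives onset date, time since first and last dose, and intensity. Pain scores are listed too. Timing can therefore be read subject by subject, but no table aggregates it.

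A third inference, that the drug–placebo difference would be understated, fails on step 4 of the working.

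Three practical objections carry some weight:
- No document promises a by-visit summary. Listings and adverse-event tables arguably meet the letter of Protocol 8.8. They still leave the repeated-administration question without an aggregate answer.
- The case report form is not among the documents, so a graded field per visit is not confirmed. The detailed table shells are in a separate document (SAP 9.1.1).
- Part 2 was added after Part 1 enrolment was complete, and the SAP is dated 17 December 2021. Rewording Protocol 9.1 cannot restore Part 1 reactions that were never entered as adverse events. A table drawn from the evaluation can recover them only if the evaluation was captured separately.

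**Conclusion.** The point holds as a cheap improvement, not as a correction of an invalid analysis. For a named repeated-administration endpoint, the SAP chooses a source and a set of tables without a visit dimension, while the protocol schedules and records an evaluation at all 13 treatment visits. That rests on the text alone. It affects 780 scheduled evaluations in Part 1 and 390 in Part 2, assuming 60 and 30 subjects with full attendance.

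The possible omission of reactions from every summary depends on how sites read Protocol 9.1 against 9.2, and its size is unknown. The 20% and 40% example shows only that an ever/never count can conceal recurrence; it predicts nothing about this trial.

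**What to change.** In SAP 9.3.7, replace the sentence that routes reactions through the adverse-event data with text to this effect: *Injection-site reactions are summarised from the scheduled post-injection evaluation (Protocol Table 4-2) as recorded. By arm and visit T1–T13, the table shows n (%) of subjects injected at that visit who had any reaction, and the CTCAE grade where recorded. It also shows the overall n (%) of subjects with any reaction. Reactions coded as TEAEs are shown separately.*

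Reconcile Protocol 9.1 with 9.2 on whether every observed reaction is entered as an adverse event, and state in the SAP how Part 1 data already collected are to be read. Before finalising the shell, confirm what the case report form holds for each visit.

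The cost is one extra table from an assessment already scheduled, with no change to any study procedure. The downside is that reported reaction rates may look less favourable.
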